9.4 APPROPRIATENESS OF MEASUREMENTS

The efficacy and safety assessments used in this study are standard for the evaluation of therapy in patients with asthma

10 STUDY PROCEDURES

10.1 VISIT SCHEDULE

The clinical study consists of 3 periods:

- 1. Screening and OCS Optimization Period (from 3 to up to 8 weeks for those patients who experience an asthma exacerbation that requires a change in OCS dose this period can be extended to 10 weeks to allow for 2 weeks of stabilization prior to randomization; Visits 1 and 2)
- 2. Treatment Period (24 weeks): includes the randomization visit (Visit 3) and a 4-week induction phase (Visits 4 and 5), a 16-week OCS reduction phase (Visits 6-10), and a 4-week maintenance phase (Visit 11)
- 3. Post-treatment Period (12 weeks; Visits 12-14)

The study visits occur on the planned dates (relative to the first injection), as scheduled. After randomization, the visit schedule should be adhered to within the ± 3 day visit window.

Patients who permanently discontinue the study medication will be asked and encouraged to return to the clinic for all remaining study visits and participate in follow-up assessments according to the visit schedule. Under exceptional circumstances when a patient cannot come to the site for the scheduled visit/s, a phone contact can be made after sponsor approval is given. During the phone contact information about AEs, concomitant medications and exacerbation events should be collected.

Patients should be reminded that sexually active female patients of reproductive potential are required to practice effective contraception during the entire study duration, while taking dupilumab and for 12 weeks post last IMP dose.

Prior to all screening assessments, after discussion of participation in the study, the written consent form (including voluntary participation in pharmacogenetic testing/future use of blood samples) must be signed and dated.

Although the screening assessments for this study are grouped under the heading of 2 visits in this protocol, it is possible for them to be performed over more than the 2 scheduled site visits if necessary, as long as the screening window prior to randomization (Day 1) is respected. If certain dynamic laboratory tests do not meet the eligibility criteria, these laboratory assessments may be repeated, at the discretion of the Investigator, if it is judged to be likely to return to acceptable range for study inclusion within the screening visit window prior to Day 1. These patients do not need to sign a new ICF and be allocated a new patient number within this same screening window.

Patients that fail the initial screening for exclusion criteria, eg, concomitant medications, may be rescreened for study eligibility 1 additional time. Patients that are rescreened must sign a new

consent form and all of the Visit 1 procedures must be repeated (refer to Section 8.4 for further instructions related to rescreening) unless a prior assessment is performed within the time frame permitted prior to study entry.

Patients who fail the Screening Visit because of eDiary/spirometry equipment malfunction, or patient-related/site personnel-related unintentional errors may be rescreened 1 time after approval is granted by the Sponsor's clinical study director. In every case of rescreen allowance due to technical equipment malfunction and/or unintentional human error(s), the Study Investigator must document receipt of Sponsor approval and, when applicable, document the site's corrective action plan to prevent future occurrences.

All clinical assessments and blood samples should be performed/collected prior to the administration of the IMP, unless otherwise specified.

For patients at select sites in Canada who have agreed to participate in the optional assessment, a sputum sample will be collected at the time of an asthma exacerbation during an unscheduled visit.

10.1.1 Screening and Oral Corticosteroid Optimization Period

Patients who meet eligibility criteria at the Screening visit (Visit 1) will enter the OCS Optimization phase. The Screening/OCS Optimization Period will be from 3 to up to 8 weeks (if an asthma exacerbation occurs that requires a change in OCS dose this period can be extended to 10 weeks to allow for 2 weeks of stabilization prior to randomization) in duration, dependent upon the length of time the patient requires to optimize their OCS dose.

Prednisone or prednisolone will be used as the OCS. At the Screening visit, patients currently using other forms of maintenance OCS must have their corticosteroids switched to the corresponding equivalent daily dose of prednisone/prednisolone.

Follow up visits/phone calls may be added during this period depending on the patient's response to OCS dose changes.

10.1.1.1 Visit 1 (Week -8 to -3)

Following a discussion of participation in the clinical trial, informed consent must be obtained and documented. These steps precede any study procedures. In patients who experience an asthma exacerbation during the OCS Optimization phase, this visit may occur at Week -9 or -10.

The following procedures will then be performed:

- Call IVRS/IWRS to assign patient number and register screening visit
- Interview to collect patient demographic information including gender, ethnic origin, race, date of birth, height, weight, and body mass index (BMI).
- Collect other medical history and surgical history, and prior and concomitant medications

- Medical history will include smoking status; history of diabetes, hypertension, sinusitis, polyposis, osteoporosis, cataracts, aspirin sensitivity, previous intubations, asthma exacerbations in the previous years, gastrointestinal bleeding, myopathy, signs of adrenal insufficiency/crisis, and susceptibility to infections; and triggers of worsening asthma.
- Therapy history should include current treatments for asthma including the duration of prior use of maintenance OCS for the treatment of asthma, coursed of rescue corticosteroid (oral or parenteral).
- Review entry criteria to assess eligibility, with special attention to verify the following:
 - Patients must be on a stable dose high-dose ICS (fluticasone propionate >500 µg total daily or equipotent) plus a second controller (LABA, LTRA, etc.) for ≥1 month prior to Visit 1. In addition, patients requiring a third controller for their asthma are considered eligible for this study. The third controller should also be used for at least 3 months with a stable dose ≥1 month prior to Visit 1.
 - Patients should be on a well-documented, regular prescribed treatment of maintenance systemic corticosteroids in the 6 months prior to Visit 1 with a stable OCS dose for the 4 weeks prior to Visit 1. Patients must be taking 5-35 mg/day of prednisone or equivalent at Visit 1.
- Measure vital signs (blood pressure, heart rate, respiration rate, body temperature, weight [kg], height [cm])
- Perform physical examination including an assessment for any clinically significant adverse effects associated with the use of maintenance OCS.
- Perform a nasal exam to check for the presence/absence of nasal polyps.
- Dispense eDiary and PEF meter, provide instructions for daily use, and remind patient to bring the eDiary to the next visit.
- Instruct the patient on how to complete the ACQ-5. The first ACQ-5 will be collected at Visit 1 and then weekly thereafter throughout the duration of the study.
- Administer the following PROs:
 - AQLQ
 - HADS
 - EQ-5D-5L
 - SNOT-22 (only for patients with bilateral nasal poilyposis/chronic rhinosinusitis)
- Complete the Health Resource Utilization questionnaire
- Measure FeNO
 - Exhaled nitric oxide assessment is conducted prior to spirometry and following a fast of ≥ 1 hour
- Perform spirometry

Entry criteria at Visit 1 include the requirement of a specific FEV_1 and demonstration of reversibility as specified in Section 7.1. See below for additional directions.

- Spirometry will be performed in the morning if possible, but if the testing can only be done at a different time of the day, the testing should be done at approximately the same time of the day at each visit throughout the study, after withholding the last dose of salbutamol/albuterol or levosalbutamol/levalbuterol for at least 6 hours and withholding the last dose of LABA for at least 12 hours and withholding the last dose of LAMA for at least 24 hours.
- Pre-bronchodilator FEV₁ must be <80% predicted normal for adults and \leq 90% of predicted normal for adolescents.
- Establish reversibility
 - Reversibility must be at least 12% and 200 mL in FEV₁ after 200 µg to 400 µg (2 to 4 puffs of albuterol/salbutamol, or levalbuterol/levosalbutamol, or of a nebulized solution of albuterol/salbutamol or levalbuterol/levosalbutamol. (Note: This is only required if reversibility or airway responsiveness was not performed within 12 months prior to Visit 1.)
 - Three total attempts may be made during the Screening Period to meet the qualifying criteria for reversibility.
- Perform 12-lead ECG
- Perform chest X-ray or magnetic resonance imaging (MRI), as per local standard of care, if no chest imaging (X-ray, computed tomagraphhy [CT], MRI) is available from the previous year or if there is local requirement.
- Obtain blood samples for screening clinical laboratory determinations:

Hematology (see Section 9.2.3.5 for details)

- Serum chemistry (see Section 9.2.3.5 for details)
- Obtain blood samples for hepatitis screen (HBsAg, HBsAb, IgM and IgG/total-HBcAb, and HCVAb), HIV screen (anti-HIV-1 and anti-HIV-2 antibodies), and anti-nuclear antibody (ANA). Patients who are IgG/total-HBcAb positive and HBsAg negative at Visit 1 must undergo HBV DNA testing prior to randomization to determine eligibility (only applicable for patients who plan to roll over into a long term study). In case of results showing HCVAb positive, HCV RNA testing must be negative/not detected prior to randomization.
- Obtain blood sample for serum immunoglobulins (total IgG, IgM, and IgA)
- Perform parasitic screening if there is a clinical suspicion per Investigator judgment (to be done using local testing as per local guidelines).
- Obtain serum β-human chorionic gonadotropin (β-HCG) pregnancy test if female of childbearing potential
- Obtain urine for urinalysis (dipstick). If any parameter on the dipstick is abnormal, a urine sample should be sent to the central laboratory for testing.

- Record any AEs/SAEs
- For those patients who were previously receiving an OCS other than prednisone or prednisolone, switch their OCS to the equivalent daily dose of prednisone/prednisolone (see Appendix A).
- Dispense salbutamol/albuterol or levosalbutamol/levalbuterol for use as reliever medication throughout the study. Instruct patient to record usage in the electronic diary.
- Remind patient to continue their controller medication (including OCS and ICS in combination with 1 or 2 other controllers) and instruct patient to record daily usage in the electronic diary.
- Remind patient to withhold last dose of salbutamol/albuterol or levosalbutamol/levalbuterol for at least 6 hours and withhold last dose of LABA for at least 12 hours and withholding the last dose of LAMA for at least 24 hours prior to next visit.

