- *q* OCS titration during the OCS Optimization Phase can occur weekly following Visit 2 until the optimal OCS dose is determined and every 4 weeks during the OCS Reduction Phase but is not necessarily required to occur during a scheduled in-clinic visit.
- r At the EOT visit (Visit 11), the final OCS dose the patient is receiving needs to be documented; no adjustments to the OCS dose will be permitted (except for those patients who experience an asthma exacerbation).
- s Serum pregnancy test at Visit 1 and urine pregnancy tests at other visits. A negative result must be obtained at Visits 1 and 3 prior to randomization.
- t Hematology: hemoglobin, hematocrit, platelet count, total white blood cell count with 5-part differential count, and total red blood cell count. Serum chemistry: creatinine, blood urea nitrogen, glucose (only at Visits 3, 8, and 11), HbA1c, uric acid, total cholesterol, total protein, albumin, total bilirubin (reflex testing will be triggered by elevated bilirubin), alanine aminotransferase, aspartate aminotransferase, alkaline phosphatase, lactate dehydrogenase, electrolytes (sodium, potassium, chloride), bicarbonate, and creatine phosphokinase. Clinical laboratory testing at Visit 1 and Visit 10 (only for patients who planned roll over into a long-term study) includes hepatitis screen (HBsAg, HBsAb, IgM and IgG/total-HBcAb, and HCVAb), HIV screen (anti-HIV-1 and anti-HIV-2 antibodies), and ANA. Patients who are IgG/Total-HBc Ab positive and HBs Ag negative at Visit 1 must undergo HBV DNA testing prior to randomization to determine eligibility (only applicable for patients who plan to roll over into a long term study). Note: Anti-ds DNA antibody will be tested if ANA is positive (≥1:160 titer). At Visits 3 (randomization), 8, and 11, the blood sample should be taken with the patient in fasting state which means no intake of any food or drink except for water for at least 8 hours. If the visit can only be done at a different time of the day and the patient is not fasting, then he/she should be advised to eat a light meal and the site should document that serum chemistry was not obtained under fasting conditions.

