- E 28. Evidence of acute or chronic infection requiring treatment with antibacterials, antivirals, antifungals, antiparasitics, or antiprotozoals within 4 weeks before Visit 1, significant viral infections within 4 weeks before Visit 1 that may not have received antiviral treatment (eg, influenza receiving only symptomatic treatment). Exceptions may be considered for uncomplicated mild viral or fungal infections requiring antiviral or antifungal therapy respectively only after discussion with the Investigator and approval by the Sponsor.
- E 29. Live, attenuated vaccinations within 4 weeks prior to Visit 1 or planned live, attenuated vaccinations during the study; see Appendix B for list of prohibited live, attenuated vaccines.
- E 30. Patients with active autoimmune disease or patients using immunosuppressive therapy (including OCS) for an autoimmune disease (eg inflammatory bowel disease, primary biliary cirrhosis, systemic lupus erythematosus, multiple sclerosis) or patients with high titer of autoantibodies at Screening who are suspected by the Investigator or the Sponsor of having a high risk for developing an autoimmune disease.
- E 31. History of malignancy within 5 years before the Screening visit, except completely treated in situ carcinoma of the cervix, completely treated and resolved nonmetastatic squamous or basal cell carcinoma of the skin.

- E 32. Patients with a history of systemic hypersensitivity reaction, other than localized injection site reaction, to any biologic drug.
- E 33. Patients with:
 - Positive (or indeterminate) test for hepatitis B surface antigen (HBs-Ag),
 - Positive IgM hepatitis B core antibody,
 - Positive IgG/total hepatitis B core antibody confirmed by positive hepatitis B virus DNA (HBV DNA)
 - Positive hepatitis C virus antibody (HCVAb) confirmed by positive hepatitis C virus RNA (HCV RNA)
- E 34. Patient has evidence of liver injury, as defined by any of the following criteria:
 - Clinically significant/active hepatobiliary disease
 - Alanine aminotransferase $>3 \times$ upper limit of normal (ULN)
- E 35. Patient has any of the following abnormal lab values at Screening:
 - Creatine phosphokinase $>10 \times ULN$
 - Platelets <100,000 cells/mm³
 - Eosinophils >1500 cells/mm³

7.2.4 Additional exclusion criteria during or at the end of the Screening period/OCS optimization period before randomization

- E 36. Patient who has withdrawn consent before enrollment/randomization.

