- Serum immunoglobulins: quantitative immunoassays for total IgG, IgG subclasses 1-4, IgM, and IgA (after the first administration of IMP, results are blinded to the sites and sponsor study team).

Amended Clinical Trial Protocol 02 EFC13691 - dupilumab 25-Jan-2017 Version number: 1

• Clinical laboratory testing at Visit 1 and Visit 10 adds hepatitis screen including HBsAg, HBsAb, IgM and IgG/total-HBcAb, HCVAb, HIV screening (anti-HIV-1 and anti-HIV-2 antibodies), and anti-nuclear antibody (ANA). Note: anti-double-stranded DNA antibody will be tested if ANA is positive (≥1:160 titer). Patients who are IgG/total-HBcAb positive and HBsAg negative at Visit 1 must undergo HBV DNA testing prior to randomization to determine eligibility (only applicable for patients who plan to roll over into a long term study). In case of results showing HCVAb positive, HCV RNA testing must be negative prior to randomization.

Decision trees for the management of certain laboratory abnormalities by Sanofi are provided in Appendix F.

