10.6.4 Elevated liver function tests

No preclinical and clinical data has suggested any hepatic toxicity of dupilumab; however, as a general consideration of clinical development, the administration of immunosuppressant or immunomodulating agents may represent an additional risk factor for hepatotoxicity.

In order to closely follow potential liver function abnormalities, assessment of total protein, albumin, total bilirubin, ALT, aspartate aminotransferase, and alkaline phosphatase are measured as part of the clinical laboratory testing. Clinical laboratory testing at Visit 1 and Visit 10 (only applicable for patients who planned to roll over into a long-term study) adds hepatitis screen (HBsAg, HBsAb, IgM and IgG/total-HBcAb, and HCVAb). Patients who are IgG/total-HBcAb positive and HBsAg negative at Visit 1 or Visit 10 must undergo HBV DNA testing prior to randomization to determine eligibility (only applicable for patients who plan to roll over into a long-term study). Furthermore, it is recommended that patients who are receiving potentially immunosuppressive therapy and are IgG HBcAb positive and HBV DNA negative undergo surveillance HBV DNA studies every 1 to 3 months depending upon the individual potential therapeutic risk and comorbidities. If necessary, a hepatologist should be consulted on a case-by-case basis.

Hepatitis virus tests and liver function tests (LFTs) will be performed at Visit 1, prior to randomization, to exclude those patients with high risk of hepatitis infection or severe liver injury from this study (Section 7.2 and Section 9.2.3.5).

In order to closely follow potential liver abnormalities, assessment of total protein, albumin, total bilirubin (in case of values above the normal range, differentiation in conjugated and nonconjugated bilirubin), alanine aminotransferase, aspartate aminotransferase, and alkaline phosphatase are measured as part of the clinical laboratory testing (Section 9.2.3.5).

Guidance for the investigation of elevated LFTs is provided in Appendix F.

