2.1.4.3 Laboratory safety variables

Clinical laboratory data consists of blood analysis, including hematology, clinical chemistry, serum immunoglobulins, and urinalysis. Clinical laboratory values after conversion will be analyzed into standard international units and international units will be used in all listings and tables.

Blood samples for clinical laboratories will be taken at Visits 1 (Week -8 to -3), 3 (Week 0), 5 (Week 4), 7 (Week 8), 8 (Week 12), 9 (Week 16), 10 (Week 20), 11 (Week 24), 14 (Week 36), and early termination unless otherwise specified. The laboratory parameters will be classified as follows:

- Hematology
 - **Red blood cells and platelets and coagulation**: hemoglobin, hematocrit, platelet count, total red blood cell count
 - White blood cells: total white blood cell (WBC) count, neutrophils, lymphocytes, monocytes, basophils, eosinophils
- Clinical chemistry
 - **Metabolism:** glucose, hemoglobin A1c (HbA1c), total cholesterol, total protein, albumin, creatine phosphokinase
 - Electrolytes: sodium, potassium, chloride, bicarbonate
 - Renal function: creatinine, blood urea nitrogen, uric acid
 - **Liver function**: ALT, aspartate aminotransferase (AST), alkaline phosphatase, lactate dehydrogenase, total bilirubin (in case of values above the normal range, differentiation in conjugated and non-conjugated bilirubin)

- **Pregnancy test**: A serum pregnancy test (β-human chorionic gonadotrophin) will be performed at Screening (Visit 1, Week -8 to -3) in women of childbearing potential
- **Hepatitis screen** (at Visits 1 [Week -8 to -3] and 10 [Week 20]): hepatitis B surface antigen (HBsAg), hepatitis B Surface antibody (HBsAb), Immunoglobulin M (IgM) and Immunoglobulin G (IgG)/total-hepatitis B core antibody (HBcAb), hepatitis C antibody (HCAb). Patients who are IgG/total-HBcAb positive and HBsAg negative at Visit 1 must undergo HBV DNA testing prior to randomization to determine eligibility. In case of results showing HCVAb positive, HCV RNA testing must be negative prior to randomization.
- **HIV screening** (at Visits 1 [Week -8 to -3] and 10 [Week 20]): anti-HIV-1 and HIV-2 antibodies
- Anti-nuclear antibody (ANA) (at Visits 1 [Week -8 to -3] and 10 [Week 20]). Note: anti-double-stranded DNA antibody will be tested if ANA is positive (≥1:160 titer).

Serum immunoglobulins

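### Visit 1 HBV DNA testing is required only of patients planning rollover, so a candidate whose E33 status depends on that result can be randomized without it

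*Protocol*

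**What the plan says.** Protocol 7.2.3, E33, handles viral hepatitis in four parts. A positive or indeterminate HBsAg excludes the patient outright, and so does a positive IgM core antibody. The third part needs a second test: "Positive IgG/total hepatitis B core antibody confirmed by positive hepatitis B virus DNA (HBV DNA". The fourth treats hepatitis C in the same way, with antibody confirmed by RNA. None of the four parts mentions the long-term study.

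The Visit 1 list in Protocol 10.1.1.1 takes up candidates with a positive IgG/total core antibody and a negative HBsAg; these, it says, "must undergo HBV DNA testing prior to randomization to determine eligibility (only applicable for patients who plan to roll over into a long term study". Footnote t to the flow chart (Protocol 1.1) limits the rule in the same way, again by reference to rollover: "HBs Ag negative at Visit 1 must undergo HBV DNA testing prior to randomization to determine eligibility (only applicable for patients who plan". Protocol 9.2.3.5 repeats rule and limit. Protocol 10.6.4 applies both to two visits at once, for patients "negative at Visit 1 or Visit 10 must undergo HBV DNA testing prior to randomization to determine eligibility".

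SAP 2.1.4.3 states the rule with no limit: "Patients who are IgG/total-HBcAb positive and HBsAg negative at Visit 1 must undergo HBV DNA testing prior to randomization to determine eligibility".

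For hepatitis C, Protocol 9.2.3.5 says "In case of results showing HCVAb positive, HCV RNA testing must be negative prior to randomization", again with no limit. Protocol 10.6.4 describes the Visit 1 hepatitis and liver tests as intended "to exclude those patients with high risk of hepatitis infection or severe liver injury from this study".

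**The concern.** An eligibility criterion and the procedure that supplies its data should cover the same patients. Here the criterion covers every candidate and the procedure covers a subset, defined by something unrelated to the risk. A rollover plan is also a weak basis for the split: rollover comes only after the 24-week treatment period (Protocol 8.2.6 and 10.1.3), and the Visit 1 procedure list has no step that records the intention.

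What is at stake is patient safety. A patient with unrecognized HBV DNA positivity could start up to 24 weeks of an immunomodulator while taking 5 to 35 mg/day of prednisone at entry. Protocol 10.6.4 accepts that immunomodulating agents may add to hepatotoxic risk. Its monitoring advice is worded for patients on potentially immunosuppressive therapy who "are IgG HBcAb positive and HBV DNA negative undergo surveillance HBV DNA studies every 1 to 3 months". A patient who was never tested is not known to be DNA negative, and so is not clearly covered by that advice.

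**Working it through.** There is no figure to reproduce. The check sets the statements side by side and follows one candidate through them.

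**Step 1. Where each Visit 1 confirmation rule is stated, and whether it is limited to rollover patients**

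| Place | HBV DNA rule | HCV RNA rule |
|---|---|---|
| Protocol 1.1, footnote t | limited | not stated |
| Protocol 9.2.3.5 | limited | no limit |
| Protocol 10.1.1.1 | limited | no limit |
| Protocol 10.6.4 (joint with Visit 10) | limited | not stated |
| SAP 2.1.4.3 | no limit | no limit |

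Count: HBV DNA, 4 of 5 limited; HCV RNA, 0 of 3 limited. E33 uses the same antibody-then-nucleic-acid construction for both viruses, so nothing in the criterion explains the difference.

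**Step 2. One candidate: HBsAg negative, IgM-core negative, IgG/total-core positive, no rollover plan**

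1. The HBsAg and IgM parts of E33 are not met.
2. The third part turns on HBV DNA.
3. The four protocol statements do not require HBV DNA for this patient.
4. With no result, positivity is never confirmed, E33 is not triggered, and the patient can be randomized with HBV DNA unknown.

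**Step 3. Does another provision supply the missing result?**

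- E21 (active hepatitis), E28 (infection needing antivirals within 4 weeks before Visit 1) and E34 (active hepatobiliary disease, ALT above 3 × ULN) pick up overt or treated disease. None calls for HBV DNA.
- Liver tests about every 4 weeks on treatment (flow chart) and the ALT stopping rules (Protocol 10.3.3) act only after exposure has begun.
- The hepatologist consultation in Protocol 10.6.4 is case by case and presupposes that a problem has been noticed.

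These reduce the risk. None gives the result before randomization.

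**Step 4. Visit 10**

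In Protocol 10.1.2.3.5 the hepatitis screen itself is only for patients who plan to roll over, so the limit belongs there. But that section asks for HBV DNA before randomization, which took place 20 weeks earlier. The joint sentence in 10.6.4 has the same fault. The pattern suggests, without proving, that Visit 1 and Visit 10 wording was merged.

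**Step 5. Size**

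Let p be the share of the 180 planned patients who are core-antibody positive, HBsAg negative and IgM-core negative, and r the share of those who plan rollover. At most 180 × p × (1 − r) patients would be randomized untested, and fewer if some sites order the assay anyway. The documents give neither p nor r, so no number follows. That r is below 1 is a reasonable assumption, since the protocol plans a 12-week post-treatment period for patients who do not roll over.

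**The case against.** The strongest reply is that E33 governs eligibility and is unconditional. Entry criteria are reviewed at Visits 1, 2 and 3, and an investigator cannot properly clear E33 for a core-antibody-positive candidate without the assay. On that view a parenthetical in a procedure list does not repeal the criterion. It is true that E33 is unchanged and that a site may order the test. But four places tell the site the test does not apply to this patient, and under the written procedure the confirming result never exists.

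A second reply is that the SAP is weak evidence of intent. It does not direct sites, and the same section lists the Visit 10 hepatitis, HIV and ANA tests without the rollover limit that the protocol puts on them, so it may simply be abbreviated. That criticism stands. The case rests on E33, the hepatitis C rule and the stated purpose in 10.6.4, and does not need the SAP.

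A third reply is that the risk is small. The affected group may be very small or empty, half of patients receive placebo, steroid doses come down from Week 4 where tolerated, and 10.6.4 reports no data suggesting hepatic toxicity. All of this bears on how often harm might follow. It does not reconcile the procedure with the criterion.

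**Conclusion.** The concern holds. Followed as written, the Visit 1 procedure can randomize a patient with E33 unresolved. That makes it a rule that is wrong as stated, which is more than a missing detail. The conflict in the text is countable (4 of 5 statements against 0 of 3); the number of patients is not. The conclusion assumes that some candidates have no rollover plan at Visit 1, that some sites follow the written procedure, and that no operational document outside the protocol and SAP makes the assay automatic. The point concerns eligibility and safety and should be corrected. Nothing in the sample size, alpha, primary endpoint or estimand depends on it. The Visit 10 timing error is a separate and minor wording fault.

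**What to change.** - Delete the rollover parenthetical from the Visit 1 HBV DNA requirement in footnote t, 9.2.3.5, 10.1.1.1 and 10.6.4, so that every IgG/total-core-positive, HBsAg-negative candidate is tested before randomization. SAP 2.1.4.3 needs no change on this point.
- In 10.6.4, split the joint sentence into one for Visit 1 (no limit) and one for Visit 10 (limited to rollover patients).
- For Visit 10, in 10.1.2.3.5 and the new 10.6.4 sentence, require the result before entry into the long-term study instead of before randomization. The hepatitis C RNA sentence in 10.1.2.3.5 needs the same correction.

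The cost is a protocol amendment, which under Protocol Section 15 needs IRB/IEC approval before use unless overriding safety reasons apply, plus an HBV DNA assay for each additional core-antibody-positive candidate screened. The documents do not allow that number to be estimated, but it is an assay that E33 already presupposes.
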